#### **6.7 UNSCHEDULED VISITS**

Unscheduled study visits may occur at any time if medically warranted. Any assessments performed (e.g., laboratory or clinical assessments) at those visits should be recorded in the CRF.

## 6.8 SCHEDULE OF EVENTS

Visit Days	Screening	Treatment					Follow-Up B (±4 weeks)	
	Days -28 to -1	Days † (+7 days)						
		1	3	5	7	9*		
SBRT A		X	X	X	X	X		
Informed consent	X							
Inclusion/exclusion criteria	X							
Medical history	X						X B	
Prior/concomitant medications	X						X B	
Physical Examination C	X						X B	
Radiographic Imaging	X	X D	X D	X D	X D	X D	X E	
Hematology F	X						X B	
Biochemistry G	X						X B	
Coagulation	X						X	
Pregnancy test	X							
Fiducial placement (if needed)	X							
AE assessment	X	X					X	
EORTC QLQ-30	X						X B	
FACT-Hep	X						X B	

† Starting on day 1, SBRT dose fractions are given every other day (i.e., Monday-Friday), but not administered on Saturdays, Sundays, or holidays. Dosing interruptions because of weekends and holidays will be recorded in CRF.

\*Day 9 study assessments of radiographic imaging and AE collection will serve as Early Termination and/or End of Treatment Visit.

A Scheduled SBRT visits may be delayed by no more than 7 days between each visit, or may occur earlier than scheduled by no more than 3 days.

B Follow-up assessment to occur 6 weeks following completion of SBRT then every 3 months up to 2 years post SBRT therapy

C All physical exams will include assessing weight, vital signs, and ECOG performance status. Height will be measured at screening visit only.

DCone-beam CT will be obtained prior to each SBRT fraction.

E Participants will undergo surveillance imaging (e.g., CT scan) 6 weeks following completion of SBRT and then every 3 months for the first 2 years.

F Hemoglobin, platelets and white cell count with differential white count

G Biochemistry to include renal (creatinine, urea, sodium, potassium) and liver function (AST, ALT, bilirubin)

HAEs and laboratory safety measurements will be graded per NCI CTCAE version 5.0 as well as definition of radiation-induced liver disease (Child-Pugh elevation of 2 or more). All AEs, whether gradable by CTCAE or not, will also be evaluated for seriousness. Record all AEs and SAEs occurring from the time of consent signing to 3 months following the completion of SBRT.

## 7. EFFICACY MEASURES

Where applicable, tumor response will be determined per the investigators' assessment, according to modified Response Evaluation Criteria in Solid Tumors (mRECIST).

### 7.1 DEFINITION OF EFFICACY MEASURES

Evaluable for response. The analysis population to assess efficacy endpoints (e.g., local control rate, intrahepatic disease free survival, and overall survival), will include only participants who have received at least 85% of the prescribed SBRT dose (i.e., 85% Level 0 = 34 Gy; 85% Level -1 = 30 Gy; 85% Level -2 = 25.5 Gy). Participants that experience more than 14 days of dose interruption, after having received  $\geq$  85% of the prescribed SBRT dose will be included for analysis.

#### 7.1.1 DISEASE PARAMETERS

Measurable disease. The lesion is considered as a RECIST measurable so long as the lesion can be accurately measured in at least one dimension as 1 cm or more.

HCC Target lesions. Measured in two perpendicular axes = longest diameter (long axis) and their longest perpendicular (short axis). The sum of the products of the diameters is defined ( $\Sigma$  long-axis diameter  $\times$  short-axis diameter in mm^2). Up to 6 lesions/patient, representing the largest possible number of anatomical sites, with a preference for the largest lesions and mediastinal and retroperitoneal sites.

Consider the following for cases in which lesions show partial internal necrosis:

- The measurement of the viable tumor should be performed on CT or MRI obtained in the arterial phase, when the contrast between viable vascularized tumor tissue and non-enhancing necrotic tissue is the highest.
- The longest diameter of the viable tumor is not necessarily located in the same scan plane in which the baseline diameter was measured: a thorough careful evaluation of the CT or MRI scans is required.
- The measurement of the viable tumor diameter should not include any major intervening areas of necrosis.

HCC Non-target lesions. Measurable lesions not selected as targets and non-measurable lesions. Lesion too small ( $< 10$  mm), infiltrating or atypical enhancement (non-arterial).

Malignant lymph nodes. To be considered pathologically enlarged and measurable, a lymph node longest diameter must be  $> 15$  mm or short axis  $> 10$  mm.

### 7.2 DISEASE EVALUATION

All measurements should be taken and recorded in metric notation using a ruler or calipers. All baseline evaluations should be performed as closely as possible to the beginning of treatment and never more than 4 weeks before the beginning of the treatment.

The same method of assessment and the same technique should be used to characterize each identified and reported lesion at baseline and during follow-up. Imaging-based evaluation is

preferred to evaluation by clinical examination unless the lesion(s) being followed cannot be imaged but are assessable by clinical exam.

**Conventional CT and MRI:** Participants should be followed with either contrast-enhanced spiral computed tomography (CT) – preferably with use of multi-slice scanners – or contrast enhanced dynamic magnetic resonance imaging (MRI). The administration of intravenous contrast is recommended for all CT or MRI studies if not medically contraindicated. For multidetector CT scanners that are capable of acquiring very thin slices, it is necessary to keep in mind that it is mandatory to use contiguous slices for image read and interpretation, to avoid missing small lesions. The analysis of contiguous slices with traditional 5 mm thickness and 5 mm reconstruction interval is acceptable; however, the analysis of 2.5 mm thickness slices at 5 mm intervals is not acceptable.

## 7.3 EFFICACY CRITERIA FOR TUMOR RESPONSE

### 7.3.1 EVALUATION OF TARGET LESION

**Progressive Disease (PD):** An increase of at least 20% in the sum of the diameters of viable (enhancing) target lesions, taking as reference the smallest sum of the diameters of viable (enhancing) target lesions recorded since treatment started

**Non-Progressive Disease** Any cases that do not qualify for progressive disease

### 7.3.2 EVALUATION OF NON-TARGET LESION

**Non-Progressive Disease** Any cases that do not qualify for progressive disease

**Progressive Disease (PD):** Appearance of one or more new lesions. See 7.3.2.1

Although a clear progression of non-target lesions only is exceptional, the opinion of the treating physician should prevail in such circumstances, and the progression status should be confirmed at a later time by the principal investigator.

#### 7.3.2.1 *Evaluation of New Lesions*

A new liver nodule is classified as HCC, and will therefore be declared as a progression, when its longest diameter is  $\geq 10$  mm and it presents the typical enhancement of HCC on dynamic imaging, i.e. contrast uptake during the arterial phase with portal vein/delayed phase washout. Liver lesions  $\geq 10$  mm, which do not exhibit typical enhancement dynamics may be diagnosed as HCC if they increase of  $\geq 10$  mm on subsequent scans. In this latter case, the date of progression used a posteriori will be the date of first detection of the lesion.

### 7.3.3 LOCAL CONTROL RATE

Local control is defined as the absence of progressive disease (per Section 7.3.1) within the PTV or at the PTV margin, measured from time of first SBRT dose to time of progression or transplantation, or 2 years from last SBRT dose, whichever occurs first.

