### 4.2 PARTICIPANT EXCLUSION CRITERIA

An individual who meets any of the following criteria will be excluded from participation in this study:

1. Participants have any one of the following liver tumor characteristics:
  - a. have  $> 5$  liver tumors, or
  - b. maximal diameter  $> 5$  cm
2. Complete obstruction of portal venous flow to the segment of liver that includes the target lesion
3. Prior radiotherapy to the upper abdomen or radioembolization of the liver, or prior thermal

ablation to the target lesion.

4. For fiducial marker placement:
  - a. Have a gold allergy,
  - b. Any coagulopathy preventing safe fiducial placement
5. Contraindication to both contrast enhanced MRI and contrast enhanced CT (i.e. unable to undergo follow-up imaging or SBRT treatment planning)
6. Participation in another concurrent treatment protocol
7. Participant is pregnant or breastfeeding, or expecting to conceive or father children within the projected duration of the trial, starting with the screening visit through 120 days after the last dose of trial treatment.
8. Uncontrolled intercurrent illness, including but not limited to, ongoing or active infection, symptomatic congestive heart failure, uncontrolled hypertension, unstable angina pectoris, cardiac arrhythmia, interstitial lung disease, serious chronic gastrointestinal conditions associated with diarrhea, or psychiatric illness/social situations that would limit compliance with study requirement, substantially increase risk of incurring AEs or compromise the ability of the patient to give written informed consent

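### Section 7.3.3 ties local control to the summed target-lesion rule in 7.3.1 alone, so a new HCC nodule in or at the edge of the PTV is not a local failure, and lesions outside the field may enter the sum

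*Combined protocol and SAP*

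**What the plan says.** Section 7.3.3 gives the operational definition: "Local control is defined as the absence of progressive disease (per Section 7.3.1) within the PTV or at the PTV margin". The cross-reference is to 7.3.1 and to nothing else.

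Section 7.3.1 has one route to progression: "An increase of at least 20% in the sum of the diameters of viable (enhancing) target lesions", measured against "the smallest sum of the diameters of viable (enhancing) target lesions recorded since treatment started". Every other case is non-progressive.

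Section 7.1.1 sets which lesions enter that sum: "Up to 6 lesions/patient, representing the largest possible number of anatomical sites", "with a preference for the largest lesions and mediastinal and retroperitoneal sites". It does not limit them to irradiated lesions. Section 4.2 excludes only participants with more than 5 liver tumours or a maximal diameter above 5 cm, so 2 to 5 tumours are eligible.

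New lesions are handled elsewhere. Section 7.3.2 lists as progression "Appearance of one or more new lesions. See 7.3.2.1", and 7.3.2.1 declares a new liver nodule of at least 10 mm with typical enhancement to be HCC and a progression.

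The synopsis and the Section 3.2.2 table describe the same endpoint as progression in or at the edge of the PTV, with no limit to 7.3.1. Intrahepatic PFS (7.3.4) expressly includes new disease anywhere in the liver, the PTV included. Section 9.2.3 plans a Kaplan-Meier curve for local control in the efficacy analysis set.

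**The concern.** Local control is the first-listed secondary endpoint and should describe what happens in the treated volume. Two features of the definition stand in the way.

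1. **New disease is left out.** The PTV is the gross or internal target volume plus 5 mm (Section 5.1.2), so a new nodule can appear inside it or at its edge. The endpoint names that location, but the rule that would register the nodule is not cited.
2. **The threshold is set on a participant-level sum.** If the sum includes lesions outside the PTV, the status of the irradiated lesion is mixed with that of untreated disease.

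The pilot is meant to inform a larger trial and to estimate bridging efficacy against historical controls (Section 1.3). An in-field rate that two readers could score differently from the same scans serves neither purpose well.

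**Working it through.** The plan states no target rate, power or sample size for local control, so there is no figure to reproduce. The check sets the definitions side by side and then does arithmetic on the 7.3.1 rule.

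**Step 1. A new typical HCC nodule of at least 10 mm at the PTV edge, existing lesions stable.**

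| Section | Result |
|---|---|
| 7.3.1 (the only rule cited by 7.3.3) | Existing target-lesion sum unchanged (0%): non-progressive |
| 7.3.3, read literally | Locally controlled |
| 7.3.2 and 7.3.2.1 | Progression |
| Synopsis and 3.2.2 | Progression at the PTV edge: local failure |
| 7.3.4 | Intrahepatic progression |

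Sections 3.2.2 and 7.3.3 thus give opposite answers for the same scan. Leaving the nodule out can remove or delay a local failure but never create one, so it acts in one direction. It also applies to participants with a single lesion.

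**Step 2. Growth needed in the irradiated lesion under the summed rule.** Let a be the irradiated lesion's diameter at nadir, b the summed diameter of other target lesions (stable), and g the proportional growth of the irradiated lesion. The sum changes by g × a/(a + b). Progression needs this to reach 0.20, so g = 0.20 × (a + b)/a. The sizes below are assumptions; the documents give none.

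| Irradiated a | Other b | Growth needed |
|---|---|---|
| 20 mm | 0 | 0.20 × 20/20 = 20% |
| 20 mm | 20 mm | 0.20 × 40/20 = 40% |
| 20 mm | 30 mm | 0.20 × 50/20 = 50% |
| 30 mm | 60 mm (three equal lesions) | 0.20 × 90/30 = 60% |
| 20 mm | 80 mm (five equal lesions) | 0.20 × 100/20 = 100% |

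Example: the irradiated lesion goes from 20 to 26 mm (+30%) beside a stable 30 mm lesion. The sum goes from 50 to 56 mm, +12%, and is non-progressive.

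**Step 3. The opposite error.** Keep the 20 mm irradiated lesion stable and let the untreated 30 mm lesion grow to 40 mm. The sum goes from 50 to 60 mm, +20%, and 7.3.1 is met although nothing changed in the field. If the sum is taken over all target lesions, this could be scored as local failure. The pooled rule can therefore err either way.

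**Step 4. What one misclassification is worth.** As a simple proportion with all 15 planned participants in the efficacy set, one failure is 1/15 = 6.7 percentage points: 15/15 is 100% (exact 95% CI 78.2 to 100) and 14/15 is 93.3% (68.1 to 99.8).

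**The case against.** The strongest reply on the summed rule is that 7.3.3 does not adopt 7.3.1 without limit: it asks for that progression in a stated location. The protocol also uses the term target lesion for the lesion to be irradiated (synopsis inclusion criteria; Section 4.2). On that reading only in-field lesions are summed, an untreated 3 cm lesion never enters, and the 50% figure does not arise. This reading is available, and it largely answers the dilution point. But neither 7.1.1 nor 7.3.1 states it, several irradiated lesions would still be pooled (two equal ones again give 40%), and it does not bring new nodules back in.

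A reader might go further and infer that the summed rule biases local control upward in participants with several lesions. The documents do not support that: step 3 shows an error in the other direction, and the share of participants with several lesions is not given.

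A second reply is that a new marginal nodule is not lost to the trial, since 7.3.2.1 calls it a progression and intrahepatic PFS records it. That is correct, and it would be wrong to infer that such failures go unrecorded. But intrahepatic PFS covers the whole liver and does not separate in-field from out-of-field failure, which is the purpose of a local control endpoint.

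A third reply is that the endpoint is descriptive, with no hypothesis test or decision rule in a 15-participant pilot. This stands and limits the weight of the point.

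**Conclusion.** The definition needs correcting. The firm part is the omission of new disease: followed literally, 7.3.3 scores a new HCC nodule in or at the edge of the PTV as controlled, contrary to the synopsis and 3.2.2, and this can only favour apparent local control. How often it would happen cannot be estimated from the documents.

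The second part is an ambiguity rather than a demonstrated bias. The sum is not restricted to irradiated lesions, so in participants with several lesions it can hide growth of the treated lesion or attribute growth of an untreated one to the field. The 40% and 50% figures rest on assumed sizes (2 cm irradiated, with a stable 2 or 3 cm lesion) and on the reading that pools all target lesions. With one target lesion, itself irradiated, the threshold is 20% on either reading and only the new-nodule gap remains.

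A reader might also infer that the primary result is at risk. It is not: transplant eligibility is judged by the Milan criteria (Section 7.5), which do not use the 7.3.1 sum, and the sample size in 9.3.1 rests on the chance of SBRT ineligibility. The change should be made because it is cheap and makes the endpoint measure what its name says.

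**What to change.** Reword 7.3.3 so that:

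- local failure is either growth of at least 20% over its own nadir in the viable diameter of any irradiated lesion, or a new HCC nodule meeting 7.3.2.1 inside or at the margin of a PTV;
- a participant with several irradiated lesions fails on the date the first of them fails;
- 7.3.3 and 3.2.2 state the same event;
- the summed rule in 7.3.1 is kept for overall progression only.

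The revised text should name the measurement. Section 7.1.1 describes a sum of products of two diameters, while 7.3.1 uses a sum of diameters. A lesion going from 20 × 20 to 24 × 24 mm is +20% on a single diameter but 576/400 − 1 = +44% on the product.

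The cost is wording, plus a record of which lesions were irradiated. Target-lesion diameters are already measured, and imaging is already scheduled at 6 weeks and then every 3 months, so no visits or participants are added. The downside is that a 20% threshold on one lesion is more exposed to measurement error when the lesion is small: for a 10 mm lesion it is 0.20 × 10 = 2 mm.

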### 7.3.4 INTRAHEPATIC PROGRESSION-FREE SURVIVAL

Intrahepatic progression-free survival (PFS) is defined as the development of intrahepatic recurrent or new disease within any section of the liver, including the PTV. The consideration of whether a lesion is within or adjacent to the PTV is determined by the individual site investigator. Intrahepatic PFS is measured from time of first SBRT dose to time of progression or transplantation, or 2 years from last SBRT dose, whichever occurs first.

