Secondary Endpoints	
 
1. Incidence of progressive disease within or at the planned tumor volume (PTV) margin (i.e. local control)
 
2. Incidence of progressive disease within any section of the liver, including the PTV (e.g. intrahepatic disease free survival)
 
3. Incidence of progressive disease outside of the liver (e.g. extrahepatic disease free survival)
 
4. Overall Survival
 
5. Proportion of participants that proceed to transplantation
 
6. Incidence of non-classical radiation-induced liver disease (RILD), defined as grade 4 aspartate aminotransferase or alanine aminotransferase elevation, or an increase in CP score of <math>\geq 2</math> within 1 week to 3 months after completing SBRT.
 

	7. Incidence of liver toxicity per CTCAE v5.0 within 1 week to 3 months after completing SBRT.
Exploratory Endpoints	
 
1. QoL scores for EORTC QLQ-C30 questionnaire
 
2. QoL scores for Functional Assessment of Cancer Therapy-Hepatobiliary (FACT-Hep) questionnaire
 
3. At time of transplantation, histopathologic changes in irradiated tumor sites relative to uninvolved liver tissue will be assessed
 

Number of Participants	15
Duration of Therapy	SBRT will be administered as 5 fractions every other day (~10 day)
Duration of Follow Up	Time of progression, or transplantation, or 2-years after last SBRT dose, whichever occurs first
Key Inclusion Criteria	
 
1. Participants aged <math>\geq 18</math> years
 
2. Patient diagnosed with HCC and recommended for LTX
 
3. Meets clinical criteria for eligibility for SBRT to the target lesion
 
4. Childs-Pugh Class B8 or higher
 
5. Eastern Clinical Oncology Group performance status <math>\leq 2</math>
 
6. Safe radiation treatment planning parameters that adhere to all organs at risk constraints per section 5.1 of the protocol. If normal organs at risk constraints (including at least 700cc of uninvolved liver) are unable to be met at the lowest dose modification (30 Gy in 5 fractions), the patient is deemed ineligible for SBRT and deemed a screen failure.
 

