##### 3.2.2 SECONDARY ENDPOINTS

Endpoint	Start	End
1. Localized control rate: Incidence of progressive disease within or at the planned tumor volume (PTV) margin		Time of progression, transplantation, death or 2-years after last SBRT dose, whichever occurs first.
2. Incidence of intrahepatic progressive disease		
3. Incidence of extrahepatic progressive disease		
4. Proportion of participants that proceed to transplantation	First dose of SBRT	
5. Overall Survival		Time of death or 2-years after last SBRT dose
6. Incidence of non-classic RILD, defined as grade 4 aspartate aminotransferase or alanine aminotransferase elevation, or an increase in CP score of $\geq 2$ within 1 week to 3 months after completing SBRT (Appendix A)		3 months after last SBRT dose

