### 7.3.5 OVERALL SURVIVAL

OS is defined as the time after having completed at least 85% of the prescribed SBRT dose up to time of death, or 2 years from last SBRT dose, whichever occurs first.

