#### 9.2.3 ANALYSIS OF THE SECONDARY ENDPOINTS

Using the efficacy analysis set, the estimate of local control rate, intrahepatic progression free survival, and overall survival, will be plotted using Kaplan-Meier curve and reported with median survival and 95% CI if available. Using the same efficacy analysis set, the proportion of participants that proceed to transplantation, will be measured and reported with 95% CI.

Non-classic RILD, liver toxicity defined as a  $\geq 2$  increase in CP score (**Appendix A**), and liver toxicity per CTCAE v5.0, will be estimated along with an exact CI using the safety analysis set.

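### Intrahepatic progression-free survival is defined by intrahepatic disease alone, so a death without progression is not a failure and the reported curve and median would be too high

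*Combined protocol and SAP*

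**What the plan says.** The endpoint is described differently in four places.

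- **Section 7.3.4** calls it intrahepatic progression-free survival and says that it "is defined as the development of intrahepatic recurrent or new disease within any section of the liver, including the PTV". On timing: "Intrahepatic PFS is measured from time of first SBRT dose to time of progression or transplantation, or 2 years from last SBRT dose", whichever is first. Death does not appear.
- **Section 3.2.2** lists it as "Incidence of intrahepatic progressive disease". The end of observation is "Time of progression, transplantation, death or 2-years after last SBRT dose, whichever occurs first". Death is there, next to transplantation, and neither is labelled an event or a censoring time.
- **The synopsis** also gives an incidence but attaches a survival label: "Incidence of progressive disease within any section of the liver, including the PTV (e.g. intrahepatic disease free survival". Section 7.1 uses the same disease-free label.
- **Section 9.2.3** plans the analysis on the efficacy set: "intrahepatic progression free survival, and overall survival, will be plotted using Kaplan-Meier curve and reported with median survival and 95% CI if available". It gives no event rule, no censoring rule and no competing-risk method.

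By contrast, Section 7.3.5 does name death for overall survival, which runs "up to time of death, or 2 years from last SBRT dose, whichever occurs first". Section 9.4 rules out imputation but does not say how a death before progression enters a time-to-event analysis.

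**The concern.** A reader takes progression-free survival to mean alive and free of progression. The event in Section 7.3.4 is tumor only. A participant who dies of liver decompensation with no intrahepatic progression is therefore not a failure. Such a participant is either removed from the risk set at death (the natural reading of Section 3.2.2) or, if Section 7.3.4 is read literally, carried as progression-free to 2 years.

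Death without progression is plausible here. Eligibility starts at Child-Pugh B8, the required life expectancy is only more than 12 weeks (Section 4.1), and Section 1.4.1 says that natural hepatic decline is hard to tell from treatment toxicity. Section 1.3 says the pilot is to help develop a larger multi-institutional trial. A PFS figure that leaves out deaths would give that planning too favorable a starting value.

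**Working it through.** **The plan's own figures.** None is stated for this endpoint. The only design figure is the sample size of 15 (Section 9.3.1), which does not bear on this point. It reproduces: ln(0.05)/ln(0.80) = 13.4, rounded up to 14, and 15 patients give 1 − 0.8^15 = 96.5%.

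**Direction.** Compare a Kaplan-Meier curve that censors progression-free deaths with one that counts them as failures. The risk sets are the same at every time and the second has extra failures, so the first can never lie below it. It is strictly higher after the first progression-free death.

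A constructed example with 15 participants: progressions at months 3, 6, 10 and 15, progression-free deaths at months 4, 8, 12 and 18, and no other losses.

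- Deaths censored: 14/15 × 12/13 × 10/11 × 8/9 = 69.6%, median not reached.
- Deaths as failures: 7/15 = 46.7%, median 18 months.

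**Size, by illustration.** Inputs:

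- Median overall survival 17.0 months, the Child-Pugh B figure from a cited phase 1-2 trial (Section 1.2.1). Implied hazard: ln2/17.0 = 0.0408 per month.
- Intrahepatic progression by 12 months, in the absence of death, of 20%, 30% or 40%. This is assumed. Section 1.1 gives 20-30% progressing beyond the Milan criteria while waiting, which is a different quantity and only a rough anchor.
- Hazard of death without progression at 25%, 50% or 100% of 0.0408. This is assumed. Overall survival includes deaths after progression, so 100% is an upper bound for that survival figure.
- Constant hazards and no transplantation.

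Formulas: hp = −ln(1 − p)/12; deaths censored, S(12) = exp(−12·hp) and median = ln2/hp; deaths counted, S(12) = exp(−12·(hp + hd)) and median = ln2/(hp + hd).

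For p = 30%: hp = 0.0297. With hd = 0.0408, S(12) = exp(−12 × 0.0705) = 0.429 and the median is 0.693/0.0705 = 9.8 months, against 0.700 and 23.3 months with deaths censored.

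| Progression at 12 mo | 12-mo value, deaths censored | Deaths counted (25% / 50% / 100%) | Gap, points | Median, deaths censored (mo) | Median, deaths counted (mo) |
|---|---|---|---|---|---|
| 20% | 80.0% | 70.8 / 62.6 / 49.0% | 9.2 / 17.4 / 31.0 | 37.3 | 24.1 / 17.8 / 11.7 |
| 30% | 70.0% | 61.9 / 54.8 / 42.9% | 8.1 / 15.2 / 27.1 | 23.3 | 17.4 / 13.8 / 9.8 |
| 40% | 60.0% | 53.1 / 47.0 / 36.8% | 6.9 / 13.0 / 23.2 | 16.3 | 13.1 / 11.0 / 8.3 |

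**If a tumor-only quantity is meant.** The 12-month cumulative incidence of progression with death competing is hp/(hp + hd) × [1 − exp(−12·(hp + hd))]. For p = 30% this is 28.3%, 26.8% or 24.1%, while one minus the death-censored Kaplan-Meier value is 30%. Renaming the endpoint while keeping the same estimator would therefore overstate the incidence of progression. The complements, 71.7%, 73.2% and 75.9%, are what the literal reading of Section 7.3.4 (deaths carried as progression-free) would report as PFS.

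**The case against.** The strongest counter-argument is that no text tells the analyst to censor deaths. Section 3.2.2 puts death in the same list as progression without giving either a role, and an analyst who takes the term progression-free survival at face value in Section 9.2.3 would count deaths. This stands to the extent that censoring is an inference from the event definition. A reader might infer that the plan instructs deaths to be censored; it does not. But counting them would mean departing from the only definition that the protocol gives.

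Second, the synopsis and Section 3.2.2 both describe an incidence, so the error may lie in the label rather than in the event. That is a fair reading, and it is why the remedy offers two routes. It does not rescue the present text, because Section 9.2.3 would still report a PFS curve and median.

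Third, a reader might take 70% against 43%, or medians of 23.3 against 9.8 months, as the size of the problem. The documents do not support that: this scenario applies the whole overall-survival hazard to progression-free participants. Transplantation, which ends observation, is also left out of all the scenarios.

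Fourth, a reader might infer that the protocol will set this PFS against published PFS values. It cites none for intrahepatic PFS, and the historical comparison in Section 1.3 concerns bridging efficacy. Nor does any figure show that progression-free death is a main cause of failed bridging. Deaths are also reported separately as overall survival.

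**Conclusion.** The point holds. The endpoint's name, its event definition and its planned analysis disagree, and no section makes a progression-free death a failure. Followed as written, the plan reports a PFS that is too high once any participant dies without intrahepatic progression. That direction does not depend on the illustration.

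The size does. Over 20-40% progression and the three death hazards, the 12-month overstatement with deaths censored is about 7 to 31 percentage points. Its upper end is a bound rather than an expectation.

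The consequence is limited. This is one secondary endpoint in a single-arm pilot of 15 with no formal hypothesis test, and no decision rule or sample size rests on it. What is affected is how the result is described and what the later trial is planned on.

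**What to change.** Use one event definition and one end-of-observation list in Sections 7.3.4, 3.2.2 and 9.2.3, and bring the disease-free survival labels in the synopsis and Section 7.1 into line. Choose one of two routes:

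- **(a) Keep PFS.** Define the event as the first of intrahepatic progression or death from any cause. State how transplantation is handled, for example as censoring; at present it ends measurement with no stated role.
- **(b) Keep a tumor-only quantity.** Rename it, for example cumulative incidence of intrahepatic progression, and estimate it with death and transplantation as competing events. Do not report it as PFS or with a median survival.

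The cost is a wording amendment, which under Section 12.5 needs approval by the institutional research review committee and the IRB. No extra participants or visits are needed. Under (a) the reported PFS will be lower.

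### Section 7.3.4 words the intrahepatic PFS event as recurrent or new disease, which conflicts with the progressive-disease definition elsewhere and, read literally, leaves out growth of tumors already present at entry

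*Combined protocol and SAP*

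**What the plan says.** The plan describes this endpoint in three places.

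- Synopsis, secondary endpoint 2: "Incidence of progressive disease within any section of the liver, including the PTV".
- Section 3.2.2, endpoint 2: "Incidence of intrahepatic progressive disease".
- Section 7.3.4, the only detailed definition: "defined as the development of intrahepatic recurrent or new disease within any section of the liver, including the PTV". The same section then sets the time axis: "Intrahepatic PFS is measured from time of first SBRT dose to time of progression or transplantation, or 2 years from last SBRT dose".

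The rules these places depend on are as follows.

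- Section 7.3.1, PD of target lesions: "An increase of at least 20% in the sum of the diameters of viable (enhancing) target lesions", measured against the smallest sum since treatment started.
- Section 7.3.2, PD of non-target lesions: the one listed criterion is "Appearance of one or more new lesions". Clear progression of existing non-target lesions is left to the treating physician's opinion, with later confirmation by the principal investigator.
- Section 7.3.3: "Local control is defined as the absence of progressive disease (per Section 7.3.1) within the PTV or at the PTV margin". This section cites 7.3.1; Section 7.3.4 cites no PD rule.

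Section 9.2.3 plans Kaplan-Meier curves for local control and intrahepatic PFS in the efficacy analysis set. Section 7.4 leaves response assessment to the investigator.

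**The concern.** Recurrent or new disease is not the same event as progressive disease. A tumor that was present at entry, never disappeared and then grows is PD once the summed diameters rise by 20%. In ordinary usage it is not new, and it is hard to call recurrent. Whoever codes the events must therefore choose between the wording of 7.3.4 and that of the synopsis and 3.2.2, and the plan does not say which governs.

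The gap matters most for a baseline tumor outside the PTV. Section 4.2 excludes patients only above 5 liver tumors, and I found no statement that every tumor present at entry is irradiated. Growth of an unirradiated tumor lies outside local control by definition. If 7.3.4 does not count it either, neither liver-progression endpoint records it. Section 1.3 wants the pilot to help estimate bridging efficacy for a larger trial, so the event should be fixed before the curves are drawn.

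**Working it through.** **Plan's own figure.** The plan gives no expected value for intrahepatic PFS, so there is nothing to reproduce. The sample size of 15 (Section 9.3.1) serves below only as a denominator.

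**Step 1: a baseline tumor outside the PTV.** The sizes are assumed. At entry there is a treated lesion of 30 mm and an untreated lesion of 15 mm, both viable and both chosen as target lesions (Section 7.1.1 allows up to 6, each at least 1 cm). This patient is within Milan at entry: two tumors, each no more than 3 cm. The treated lesion stays at 30 mm and the other grows to 31 mm.

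- Reference sum: 30 + 15 = 45 mm.
- Later sum: 30 + 31 = 61 mm.
- Change: (61 − 45)/45 = 16/45 = +36%.
- The 20% threshold is 45 × 1.20 = 54 mm, reached when the untreated lesion measures 54 − 30 = 24 mm.

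| Rule | Result |
|---|---|
| 7.3.1, PD of target lesions | PD (+36%) |
| 7.5, Milan | Not met: two tumors, one above 3 cm |
| Synopsis and 3.2.2, intrahepatic PD | Event |
| 7.3.3, local control | No failure: the lesion in the PTV is stable |
| 7.3.4 read literally | No event: the growing lesion is neither new nor recurrent |
| 7.3.4, clock stops at progression | Event |

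The last two rows show that 7.3.4 conflicts with itself as well as with the synopsis and 3.2.2.

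**Step 2: effect on the estimate.** Take 15 participants, all followed, with no censoring and no deaths counted. Let

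- a = participants whose only liver progression is growth of the treated lesion in the PTV;
- b = participants whose only liver progression is a new liver lesion outside the PTV.

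Then:

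- local control = (15 − a)/15;
- intrahepatic PFS, literal reading = (15 − b)/15;
- intrahepatic PFS, any intrahepatic PD = (15 − a − b)/15.

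| a | b | Local control | Literal | Any intrahepatic PD |
|---|---|---|---|---|
| 2 | 0 | 13/15 = 86.7% | 15/15 = 100% | 13/15 = 86.7% |
| 2 | 1 | 13/15 = 86.7% | 14/15 = 93.3% | 12/15 = 80.0% |
| 2 | 2 | 13/15 = 86.7% | 13/15 = 86.7% | 11/15 = 73.3% |
| 1 | 4 | 14/15 = 93.3% | 11/15 = 73.3% | 10/15 = 66.7% |

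The counts are assumptions; the documents give none. On the literal reading, intrahepatic PFS exceeds local control only when a > b. When any intrahepatic PD counts, it never can, because 15 − a − b is at most 15 − a.

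A participant like the one in Step 1 changes neither local control nor the literal figure, but lowers the last column by 1/15.

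**Step 3: size per participant.** Each omitted event is worth 1/15 = 6.7 points. The loss at 2 years is nil if the same participant later develops a new liver lesion that does count. With censoring, a Kaplan-Meier step can exceed 1/15, because fewer participants remain at risk.

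**The case against.** The best defense is that 7.3.4 read as a whole means progression. Its title is progression-free survival, it expressly takes in the PTV, it runs to progression, and both endpoint lists count progressive disease. Nothing in the plan says that growth of a baseline tumor is excluded. Because the PTV is the tumor volume plus a 5 mm margin (Section 5.1.2), most disease inside it is the treated tumor, so the mention of the PTV would have little to do if growth there did not count. The word recurrent is undefined, and a lesion that shrinks and then regrows can fairly be called recurrent.

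Much of this stands. A reader might infer that the plan rules out PD inside the PTV as an event, so that intrahepatic PFS will come out above local control. The documents do not support that: it follows from one reading only, and then only when growth-only PTV failures outnumber patients with new intrahepatic lesions.

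A reader might also turn the 2-year local control figures in Section 1.2.1 (82% and 94%) into 6% to 18% of participants, or about 1 to 3 of 15, wrongly counted as event-free. That is at most an upper bound for the PTV mechanism. The figures come from a Child-Pugh B cohort and from a cohort of mixed cirrhosis severity, and not every local failure would be growth without a new lesion.

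Loss of Milan status within the first year is also read directly by the primary endpoint (Sections 3.2.1 and 9.2.2), so it would not go unseen.

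The defense does not remove the mismatch. Naming the PTV says where an event may occur, not which kind of change counts. The argument from regrowth does not reach an untreated tumor that has simply grown. For non-target lesions, 7.3.2 offers judgment rather than a criterion, and 7.3.4 does not refer to it.

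**Conclusion.** The inconsistency is real and worth correcting. Section 7.3.4 describes the event in terms that differ from the synopsis, from 3.2.2, from the PD rule in 7.3.1 and from its own time axis. Read literally, growth of a pre-existing tumor is not an event. The case is clearest for an untreated baseline tumor outside the PTV and weaker inside it.

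Each omitted event flatters intrahepatic PFS by up to about 6.7 points, assuming 15 participants in the efficacy set and no censoring. How often this would happen cannot be derived from the documents. The tumor sizes and event counts above are illustrations.

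Severity is minor to moderate. The endpoint is secondary and descriptive, no hypothesis is tested, and neither the sample size nor the primary analysis changes.

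**What to change.** Replace the event in Section 7.3.4 with: the first of PD of intrahepatic target lesions (7.3.1), confirmed progression of an intrahepatic non-target lesion (7.3.2), or a new intrahepatic lesion (7.3.2.1), inside or outside the PTV. Add that every local failure under 7.3.3 is also an intrahepatic event. This brings 7.3.4 into line with the synopsis and 3.2.2 and guarantees that intrahepatic PFS cannot exceed local control when both are computed on the same participants and follow-up.

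The cost is one sentence. No new data are needed, because the scheduled surveillance imaging already supplies the measurements. The intrahepatic PFS estimate may be slightly less favorable. The change should be made before the endpoint is analyzed, so that the choice of reading does not follow the results.
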